Sodium Oxybate in Treatment-Resistant REM Sleep Behavior Disorder
(RBD): A Randomized Placebo-Controlled Trial

Study Protocol

NCT04006925

July 8, 2020

Sodium Oxybate in Refractory REM Sleep Behavior Disorder: A Randomized Controlled Study.

Summary

Rapid eye movement sleep behavior disorder (RBD) is a condition resulting in violent dream-enactment during sleep which affects millions of individuals in the United States, however therapies for RBD are limited and cause significant side effects. As a result, despite using a combination of drugs, a large number of patients with RBD continue to act out violent dreams causing severe self-injuries or injuries to their bed partners. Prior studies and our own experience at Stanford have shown that sodium oxybate (SXB) can be effective in these cases of refractory RBD. This study would therefore evaluate the efficacy and tolerance of SXB in this patient population.

We propose to conduct an 8-week trial comparing SXB versus placebo randomly assigned to patients with refractory RBD, i.e. individuals who have insufficiently responded or tolerated melatonin and clonazepam. To strengthen the study design, we will use a double-blind design, and not only measure treatment efficacy based on patients, partners and clinicians report—as done in most studies; we will record RBD objective outcomes with actigraphy, a recently validated objective tool for tracking RBD activity "in vivo". In addition, our study will include the gold standard PSG-based REM activity based on video and EMG activity before and after intervention.

In summary, this study would not only address an important question from a clinical and public health perspective, it would also be the first double-blind randomized controlled study measuring a treatment response based both on clinical and physiological outcomes. We believe that this particular design should pave the way for future trials in RBD.

Scientific Basis/Rationale

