
Taken together, this suggests that SXB may be a viable treatment option in patients with isolated RBD or RBD associated with PD, who have failed MLT and CLZ due to lack of efficacy or intolerance.

Hypothesis

We hypothesize that nightly dose of SXB will result in reduction of RBD severity and frequency per patients report and objective polysomnographic and actigraphic (wrist-worn device) measures, over an 8-week double blind intervention comparing SXB and placebo (PBO). Additionally, we hypothesize that SXB improves sleep quality, and

reduces daytime sleepiness in subjects with RBD associated with a neurodegenerative condition.

Primary Objective

1. Reduction in RBD episodes frequency and severity (RBD log)

Secondary Objectives

1. Improvement in clinical global impression scores per patient and clinician (CGI- efficacy scale, CGI-E, and CGI-impression scale, CGI-I, respectively)
2. Reduction of RWAi by PSG
3. Reduction in movements severity and frequency during REM sleep by quantitative video-PSG analysis¹⁶
4. Changes in overall subjective sleepiness by Epworth sleepiness scale (ESS) and one hour after rise time by Karolinska scale
5. Tolerance and side effects to SXB and PBO

Exploratory Objectives

1. Reduction in "activity score" and "activity index" as measured by actigraphy¹⁷
2. Reduction in periodic limb movement (PLM) arousal index
3. Improved sleep quality by Pittsburgh Sleep Quality Index (PSQI)
4. Effects on mood measured by PHQ-9
5. Effects on anxiety measured by GAD-7
6. Effect on orthostatic heart rate and blood pressure (response to orthostatic maneuver)

[figure not shown]
Trial Design

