The total duration of this randomized, double-blind, placebo-controlled trial will be 2 years. For each participant the total duration of the study will be 14 weeks, including 8 weeks of intervention with SXB or PBO, preceded by a 4-week period of collection of baseline data, and followed by a 2-week period of data collection post-intervention. Subjects taking MLT or any other medication capable of affecting RBD other than clonazepam (CLZ) will maintain their regimen at fixed dose throughout the 14-week duration of the study. Those taking CLZ will proceed to reduction and discontinuation of CLZ, followed by a 2-week washout period prior to receiving study drug. If unable to discontinue CLZ prior to study drug, they will reduce CLZ to lowest acceptable dose by the end of the 4-week baseline period followed by cross-taper with SXB during the first 2 weeks of flexible dosing.

In each arm, dosage of SXB and PBO will be titrated up weekly (this weekly titration will occur via phone calls by the PI on days 2-6 after each new dose change) by up to 1.5g nightly dose increments from an initial 4.5g total nightly dose (which could be given

in two unequal doses if needed, or one single dose no greater than 4.5g) to an optimal individual dose based on clinical response on RBD symptoms and tolerability, to a maximum nightly dose of 9g ("flexible dose" period lasting up to 8 weeks). The optimal dose for each participant will then be continued for at least 4 weeks ("stable dose").

Flowchart

MOCA: Montreal Cognitive Assessment

PSG: Polysomnography

CGI: Clinical Global Impression questionnaires

- **Day 1 (Visit #1 = Initial visit with research coordinator):**
 - Verification of inclusion and exclusion criteria
 - Enrollment (if not performed prior)
 - Physical Exam (MoCA,
 - PSQI, PHQ-9, GAD-7, SCOPA-AUT, Epworth sleepiness scale
 - provide RBD logs and sleep diary for the 14 following weeks, 2 blank Karolinska scales, and two actigraphy devices (Philips Actiwatch2) to be worn on dominant wrist and ankle for one month

- instructions on when to complete Karolinska scale #1 (Day 21-27, one hour after waking up the day prior to sleep study) from home
 - Instructions on clonazepam taper, when applies
 - pregnancy testing for female subjects of childbearing age, when applicable
 - collection of adverse events (AEs)
 - MD (PI, coPI) will be available as needed via telephone or remote video conference system

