- **Day 1-28 (phone calls, weekly, when applicable):** guidance on downtitration of CLZ
- **Day 28 ± 7 days:** 1st video-PSG wearing home actigraphy device (Philips Actiwatch2) and additional wrist and ankle high-frequency actigraphy device (Xiaomi Amazfit Arc)
- **Day 29 (One day after Day 28 ± 7 days, Visit #2 = Randomization visit with research coordinator):**
 - Collection of 1-month RBD log and sleep diary
 - Collection of Karolinska scale #1
 - Collection of all actigraphy devices
 - Epworth sleepiness scale
 - Randomization
 - Subjects receive SXB or PBO and instructions on titration schedule
 - pregnancy testing for female subjects of childbearing age, when applicable
 - collection of adverse events (AEs)
 - MD (PI, coPI) will be available as needed via telephone or remote video conference system

Day 30-84 ± 7 days (phone calls): Every week after each new dose the subject will be called (including when the dose will remain stable), these phone calls will be made between day 2-6 to discuss response, record adverse events, and determine the next weeks titration dose.

- **Day 57-85 ± 7 days (Visit #3 = Interim visit with research coordinator):**
 - Collection of 1-month RBD log and sleep diary
 - Epworth sleepiness scale
 - PSQI, PHQ-9, GAD-7
 - Completion of CGI-E by participants
 - Completion of CGI-I by clinician
 - Physical Exam (including MoCA, orthostatic vital signs)
 - instructions on when to complete Karolinska scale #2 (Day 78-84, one hour after waking up the day prior to sleep study) from home
 - Participants provided with two actigraphy devices (Philips Actiwatch2) to be worn on dominant wrist and ankle for one month
 - pregnancy testing for female subjects of childbearing age, when applicable

- Collection of AEs, side effects
- MD (PI, coPI) will be available as needed via telephone or remote video conference system

- **Day 84-112 ± 7 days: 2nd video-PSG wearing home actigraphy device (Philips Actiwatch2) and additional wrist and ankle high-frequency actigraphy device (Xiaomi Amazfit Arc)**

- **Day 85-113 (One day after Day 84-112 ± 7 days, Visit #4 = Final Visit with research coordinator):**
 - Collection of high-frequency actigraphy device (Xiaomi Amazfit Arc)
 - Collection of 1-month RBD log and sleep diary
 - Collection of AEs, side effects
 - Collection of Karolinska scale #2
 - Epworth sleepiness scale
 - PSQI, PHQ-9, GAD-7, SCOPA-AUT
 - Completion of CGI-E by participants
 - Completion of CGI-I by clinician

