Participants will be randomized in a double-blind manner to either SXB or PBO. The duration of the intervention in both conditions will be no longer than 12 weeks, including up to 8 weeks of flexible dosing and 4 weeks of stable dosing. Treatment will be initiated with 4.5g dose of SXB or PBO, given nightly in two doses 2.5-4h apart according to the standard protocol used in narcolepsy. PBO will be similar in appearance, smell and flavor to the subjects, so that the investigators and participants will be unable to distinguish it from SXB. The dose will be increased or decreased by 0.5 - 1.5g weekly increments until reaching the optimal dose based on clinical response and tolerance, not exceeding 9g nightly. Evidence has shown that patients with RBD treated with sodium oxybate respond to nightly doses ranging from 3-6 g. Among these subjects, some have benefited from a 5 gram nightly dose. This flexibility in dosage is determined on an individual basis, in which the final dose must be both effective and tolerated. Dosage flexibility is essential as this older population with prodromal or overt signs of neurodegeneration may not require or tolerate the higher dosages used in patients with narcolepsy. Although the “default” regimen will be two equally divided doses 2.5-4hours apart, if required, the drug will be given in two unequal doses, or in one single dose, with no single dose allowed to be greater than 4.5g. Once optimal dose reached, fixed dose will be continued for at least 4 weeks and discontinued over one night. During the two weeks following discontinuation, data will continue to be collected. Patients will be allowed to resume usual treatment, including CLZ.

In this study, the choice of flexible dosing for patients receiving SXB is based on a few factors. From the 4 case reports summarized above, effective doses of SXB in patients with refractory RBD ranged from 3g to 6g nightly, one patient requiring uptitration of his initial 5g dose to 6g. No adverse events or side effects were reported by the authors. In patients with narcolepsy, the efficacy of SXB is dose-dependent, showing superior efficacy with 9g nightly dose compared to 6g. Taken together, this data suggests that higher SXB doses will be more likely to control RBD symptoms, however with a higher risk of side effects. In the two studies evaluating SXB efficacy and tolerance in patients with PD using flexible dosing, final mean doses were 7.8g and 4.8g^{14,15}.

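### The protocol states an 8-week intervention in a 14-week study but also schedules up to 12 weeks of treatment (about 18 weeks in all), and the second Karolinska date rule fails on the longer courses.

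*Protocol*

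**What the plan says.** **The shorter course.** The protocol's Summary says "We propose to conduct an 8-week trial comparing SXB versus placebo", and the Hypothesis section repeats the eight weeks. Trial Design says "the total duration of the study will be 14 weeks, including 8 weeks of intervention with SXB or PBO"; the other six weeks are four of baseline and two of follow-up. Trial Design and Treatment Regimen both tie the fixed background regimen (medication affecting RBD, other than clonazepam) to a 14-week study.

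**The longer course.** Trial Design also permits a flexible-dose phase of up to eight weeks, after which "The optimal dose for each participant will then be continued for at least 4 weeks". Treatment Regimen caps the sum: "The duration of the intervention in both conditions will be no longer than 12 weeks, including up to 8 weeks of flexible dosing", the remainder being four stable weeks. The Flowchart gives ranges that span both courses: Visit 3 on Day 57-85, second PSG on Day 84-112, Visit 4 on Day 85-113, Visit 5 on Day 99-127. All but Visit 4, which is set one day after the PSG, carry a 7-day tolerance either way.

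**Dependent items.**
- Logs: Visit 1 is to "provide RBD logs and sleep diary for the 14 following weeks". Visits 2, 3 and 4 each list "Collection of 1-month RBD log and sleep diary", and Visit 5 collects a two-week log.
- Karolinska: Visit 1 gives "instructions on when to complete Karolinska scale #1 (Day 21-27, one hour after waking up the day prior to sleep study"). The Visit 3 line for the second scale has the same form, with Day 78-84. The scale is listed under Secondary Endpoints.
- Supply: Treatment Regimen gives 5,292 g per arm for 12 participants and does not show how it was obtained.

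The SAP defines the per-protocol set by completion of titration and a 4-week treatment period. It states no total length, so it does not settle the matter.

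**The concern.** Treatment length is a basic design parameter. It fixes exposure, the position of the endpoint month and what completing treatment means for the per-protocol set. Flat statements of 8 and 14 weeks exclude a course that other sections of the same protocol allow and schedule.

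Some dependent items look as if they were written for the shorter course and never revisited. The sharpest case is the second Karolinska scale, which carries two timing rules that separate as the flexible phase lengthens. A site that follows the fixed days and a site that follows the day-before-PSG rule would measure the same secondary endpoint at different points of treatment. On the longest course, one measurement falls during flexible dosing and the other at the end of stable dosing.

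**Working it through.** **1. Calendar.** Let f be the number of flexible weeks. The Flowchart gives study drug at Visit 2, nominally Day 29, and four stable weeks follow the flexible phase.
- Visit 3 = Day 29 + 7f; second PSG = Day 56 + 7f; Visit 5 = Day 71 + 7f; treatment nights = 28 + 7f.
- f = 4: Visit 3 Day 57, PSG Day 84, Visit 5 Day 99, 56 nights.
- f = 8: Visit 3 Day 85, PSG Day 112, Visit 5 Day 127, 84 nights.

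These reproduce both ends of the Flowchart's ranges. Elapsed time is (99 - 1)/7 = 14 weeks for f = 4 and (127 - 1)/7 = 18 weeks for f = 8.

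**2. Second Karolinska scale.** Being on Day 78-84 and also on the day before the PSG requires a PSG on Day 79-85.

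| f | Nominal PSG | PSG with ±7 days | Days that satisfy both rules | Day before nominal PSG | Days after the fixed window (from Day 84 / from Day 78) |
|---|---|---|---|---|---|
| 4 | 84 | 77-91 | 79-85 | 83 | inside the window |
| 5 | 91 | 84-98 | 84-85 | 90 | 6 / 12 |
| 6 | 98 | 91-105 | none | 97 | 13 / 19 |
| 7 | 105 | 98-112 | none | 104 | 20 / 26 |
| 8 | 112 | 105-119 | none | 111 | 27 / 33 |

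For f = 8, using the full PSG tolerance widens the gap to between 104 - 84 = 20 and 118 - 78 = 40 days. The flexible phase then runs Day 29-84, so Day 78-84 is its last week.

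The table assumes the Day 29 start. Visit 2 follows the first PSG (Day 28 ± 7) by a day, so drug could start as early as Day 22. With that start and f = 6, the PSG is due on Day 22 + 42 + 27 = 91, and a further 7 days early is Day 84, which just fits. For f = 7 and 8 the earliest days are 91 and 98, which do not.

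**3. First Karolinska scale.** Day 21-27 and the day before the PSG require a PSG on Day 22-28. The Flowchart allows Day 21-35, so Day 21 and Days 29-35 break one rule. This comes from the visit tolerance, not from the duration conflict.

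**4. Logs.** Issued: 14 × 7 = 98 days. Collected: 4 + 4 + 4 + 2 = 14 weeks, against 18 elapsed weeks at f = 8. Visit 3 to Visit 4 is (57 + 7f) - (29 + 7f) = 28 days for every f, so the Visit 4 line covers the endpoint month on every nominal course. The mismatch lies between Visits 2 and 3: 85 - 29 = 56 nights at f = 8, against a one-month log.

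**5. Supply.** 5,292/12 = 441 g each.
- Eight weeks at the fastest stated titration to the cap: 7 × (4.5 + 6 + 7.5 + 9) + 28 × 9 = 189 + 252 = 441 g, an exact match.
- Twelve weeks on that pattern: 7 × (4.5 + 6 + 7.5 + 9 × 9) = 693 g each, 8,316 g per arm, which is 3,024 g (57%) more.
- But 441/84 = 5.25 g, so a 12-week course with that mean nightly dose uses the same amount; for example, 7 × (6 × 4.5 + 6 × 6) = 441 g.

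**6. Baseline log span (separate point).** With the first PSG on Day 21-35 and Visit 2 the next day, the baseline log covers about 21 to 35 nights. At a constant nightly rate, a raw count would be 21/28 = 75% to 35/28 = 125% of the 28-night value.

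**The case against.** **The operative schedule is coherent.** Twelve weeks is a ceiling, so an 8-week course complies with it, and the visit ranges consistently carry 4 to 8 flexible weeks plus 4 stable ones. The 8- and 14-week statements may simply be text that was not updated. This largely stands: the schedule can be run. It does not remove the conflict, because the flat statements rule out a course that is permitted. The weekly calls on Day 30-84 settle nothing, since they fit an 8-week course and an 8-week flexible phase equally well.

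**The Karolinska line contains a workable rule.** A site could ignore the fixed days and use the day before the PSG, and Visit 4 collects the scale the day after the PSG. That is so, but the line gives two rules and no precedence. It would also be tempting to say that with eight flexible weeks the instruction always comes too late. Visit 3 is nominally Day 85, but its tolerance allows Day 78, so that does not follow.

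**Stronger readings that the documents do not support.** A reader might infer that the logs run out on Day 98, inside the endpoint month of Day 85-112. That assumes the 14 weeks of logs are used consecutively, which is nowhere stated, and the Visit 4 collection line covers that month. A reader might also infer from the exact match that the drug supply fits only the shorter course and would fall short on the longer one. Since 441 g also covers 84 nights at a mean of 5.25 g, the match suggests an origin but proves neither.

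**Recording nights is a different subject.** Expressing the count per 28 nights does not follow from the duration conflict, and neither document gives a figure for missed nights. This stands. The proposal rests on the visit tolerance alone and is offered as a small, separable improvement.

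**Conclusion.** The contradiction holds on the current text. The protocol states 8 weeks of treatment and 14 weeks in all, while allowing and scheduling up to 12 and about 18. The 14-week log issue and the 14-week background-regimen wording were not extended to match, and the basis of the supply figure is unstated.

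The one endpoint rule shown to fail is the second Karolinska scale. From the nominal Day 29 start, its two timings are incompatible with six or more flexible weeks, even with the second PSG seven days early. With eight, they lie 27 to 33 days apart at the nominal PSG date. The first scale has a smaller conflict of the same kind.

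The number of participants affected is unknown, because the share needing more than four flexible weeks is not given. Both arms follow the same schedule, and no bias between arms is shown. This should be corrected, but it does not undermine the primary comparison.

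**What to change.** 1. Reconcile Summary, Hypothesis, Trial Design and Treatment Regimen to one maximum intervention length and one total duration. Which one is for the sponsor to decide.
2. Bring the log and diary issue, the Visit 3 log line and the 14-week background-regimen wording into line with that choice, and state how both 5,292 g figures were derived.
3. Define each Karolinska scale only as the day before the actual PSG and delete the fixed study days.
4. The SAP is written in the past tense, so data may already be collected. In that case, state which duration applied, and report achieved treatment weeks and the Karolinska-to-PSG interval by arm.
5. Separately, express the primary count per 28 recorded nights within the SAP's linear mixed model, and report recorded nights by arm and period.

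**Cost.** Items 1 to 3 are amendment wording, plus up to four more weeks of diary pages if the longer course is kept. Item 4 is a short table. Item 5 is one derived variable and one table. Its downsides are that it assumes unrecorded nights resemble recorded ones, and that rates over unequal numbers of nights have somewhat unequal variance. No new procedures are needed.

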Our study will include a mixed group of participants, some with a neurological diagnosis of PD and some otherwise healthy individuals. We identify risk of dizziness and falls as the most concerning risk in patients with a diagnosis of synucleinopathy, as this could be aggravated by SXB. We will therefore carefully exclude from this study any participant who already suffers from balance impairment resulting in falls or requiring an ambulating device, as well as any patient with symptomatic orthostatic hypotension. Taken all these considerations into account, and given the expected interindividual variability regarding

optimal dose of SXB, we chose flexible dosing for highest clinical benefit while minimizing the risk of side effects.

The total amount of SXB for the 12 participants randomized to active drug is: 5,292g.
The total amount of PBO for the 12 participants randomized to placebo drug is: 5,292g.

Option for “Rescue” Open Label Extension Period

All participants, should they decide to drop out of the study, may become eligible for a “Rescue” open label extension period, during which they will receive open label active drug sodium oxybate in an unblinded fashion. This will provide patients the opportunity of experiencing benefit from the study drug. Such participants would then receive ascending doses of sodium oxybate, according to the protocol, and will also be asked to present for visits and second polysomnography starting at visit 2, otherwise required by the protocol until the end of the study.

Inclusion Criteria

- Adult patients aged 40 to 85 years
- Women may be included only if they have a negative β -HCG test at screen; are sterile (documented hysterectomy, bilateral oophorectomy, or bilateral salpingectomy, or congenitally sterile) or postmenopausal (no menses for 12 months without alternative medical cause).
- Women with childbearing potential whose male partners are potentially fertile must use one of the following highly effective birth control methods for the duration of the study (ie, starting at screening) and for 30 days after last dose of study drug
 - estrogen-progestin oral contraceptive pills, patches, or vaginal ring
 - progestogen pills, implant or injection
 - intrauterine device (IUD)
 - intrauterine hormone-releasing system (IUS)
 - bilateral tubal occlusion
 - vasectomised partner (the sole sexual partner who has received medical assessment of the surgical success)or
 - abstain from heterosexual intercourse

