 1. non injurious behaviors: facial expressions, non-aggressive vocalizations (mumbling, gentle talking, casual conversation, singing, laughing...), twitches, gentle shaking, non-aggressive movements of fingers, arms or legs...;

2. potentially injurious: punching, kicking, arm flailing or thrashing around, at least one limb or head out of bed, sitting up in bed, crawling, attempting to stand up or leave bed, near falls, cursing, screaming, shouting, yelling, or any behavior requiring bed partner to wake up participant;
 3. injurious: any contact with bed partner (hitting or grabbing), wall or furniture, any fall or leaving bed (doving out, walking, jumping).
- CGI efficacy scale (CGE-E): 4-point therapeutic effect scale and 4-point side effect scale, jointly filled by patient and partner on last day of treatment
 - CGI improvement scale (CGI-I): 7-point improvement scale filled by clinician on last day of treatment
 - RWAi according SINBAR criteria comparing PSG pre-intervention to PSG post-intervention
 - video-PSG analysis of REM related vocalizations and movements (“simple” versus “complex”) as per Sixel-Döring and colleagues¹⁶
 - Sleep outcomes: EDS, Karolinska 1 h after awakening

Exploratory Endpoints

- “Activity index” as recorded by actigraphy¹⁷ (percentage of 30-second epochs with an activity score above zero) last month of treatment compared to 1-month baseline
- Sleep outcomes: PSQI
- Cognitive outcome: MoCA
- Mood and Anxiety: PHQ-9 and GAD-7
- Orthostatic vital signs

Sample Size Justification/Statistical Analysis

Sample size calculation was made for the outcome of number of RBD episodes per month. Based on the data published by Brunetti et al.¹⁸, the number of RBD episodes decreased from 11.2 \pm 5.2 at baseline to 10.3 \pm 3.7 per month in the placebo arm. To detect an effect size of 50% reduction in the number of RBD episodes per month ([placebo-active]/placebo) with a power of 80% and alpha of 5%, the number of participants would need to be 10 per arm. Based on prior studies using SXB in subjects with PD, a conservative drop out rate of 15-20% could be anticipated^{14,15}, which would require to enroll at least 24 participants, i.e. 12 participants per arm.

Reporting to Jazz Pharmaceuticals

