Sodium Oxybate in Treatment-Resistant REM Sleep Behavior Disorder (RBD): A Randomized Placebo-Controlled Trial

Statistical Analysis Plan

NCT04006925

January 11, 2023

Statistical analysis (using SAS 9.4, Cary, NC) was by intention-to-treat for the primary efficacy analysis, comparison of baseline characteristics, safety and tolerance and per-protocol (PP) for secondary/exploratory analyses. PP analysis included all participants who completed titration and the 4-week treatment period. Sample size calculation was based on a prior randomized controlled study by Brunetti et al.²⁵ To detect an effect size of 50% reduction in the number of RBD episodes per month ([placebo - active] / placebo) with a power of 80% and alpha of 5%, the number of participants needed to be 10 per arm. Anticipating a dropout rate of 20%, 24 participants required to be enrolled.

We tested the primary hypothesis that SXB is superior to placebo in reducing the number of RBD episodes from baseline, as observed in the last month of treatment using linear mixed effects models with random intercepts. Models were parameterized in two ways to estimate separate group trajectories and between-group differences in change over time. Cohen's d was calculated as a measure of treatment effect size. Similar hypotheses were tested on secondary and exploratory outcomes. Within- and between-group differences were assessed with paired- and unpaired t-tests, or with the Wilcoxon Signed Rank and Mann-Whitney U tests for nonnormal data. Bootstrapped percentile-based 95% confidence intervals were calculated based on 10,000 randomly resampled datasets. Participants scoring below 4 on the CGI-I and CGI-E were classified as "responders"; chi-square tests were performed to compare the proportion of responders between groups. All statistical tests were conducted using a 2-sided alpha level of 0.05. For secondary/exploratory analyses, bootstrapped percentile-based 95% confidence intervals were calculated based on 10,000 randomly resampled datasets. Descriptive statistics on safety data are provided for all randomized participants (intention-to-treat), by treatment group and study phase.

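### The only follow-up described after dropout is on open-label SXB, and no assessment is specified when blinded drug stops early, so the intention-to-treat primary analysis may lack usable outcomes for early stoppers

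*Protocol*

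**What the plan says.** - **After dropout.** The Protocol section on the Rescue open-label extension makes any participant who drops out, in either arm, potentially eligible for unblinded SXB. Those who take it "will also be asked to present for visits and second polysomnography starting at visit 2, otherwise required by the protocol until the end of the" trial. No other follow-up after dropout is described.
- **Scheduled collection.** In the Protocol flowchart, Visit 2 (Day 29) is the randomisation visit. The next log collection is at "Day 57-85 ± 7 days (Visit #3 = Interim visit with research coordinator"). Visit 4 and a follow-up visit come later. No early-termination visit is listed.
- **What exists between visits.** At Day 1 staff "provide RBD logs and sleep diary for the 14 following weeks", and weekly calls during treatment cover response and adverse events.
- **After the planned stop.** Under Treatment Regimen, two further weeks of data follow the end of at least four weeks of fixed dosing.
- **Primary endpoint.** Episodes in the last month of treatment are compared with a one-month baseline.
- **Analysis.** The SAP states that analysis "was by intention-to-treat for the primary efficacy analysis", using linear mixed models with random intercepts. It gives no rule for missing log months, partial logs or open-label data, and does not say whether the last month of treatment means blinded treatment.
- **Expected dropout.** In the Protocol sample size section, "a conservative drop out rate of 15-20% could be anticipated". The SAP uses 20%.

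**The concern.** An intention-to-treat comparison needs outcomes for everyone randomised, including those who stop drug. Here stopping blinded drug and leaving the study are not kept apart. A participant who stops in the first weeks of titration has no scheduled contact at which the log is handed in. If that person then takes open-label SXB, later logs are unblinded and on active drug whatever the assigned arm.

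A participant with only a baseline value adds essentially nothing to the between-group difference in change in a random-intercept model. The analysis could carry the intention-to-treat label and yet rest on those who reach Visit 3.

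Reasons for stopping plausibly differ by arm. The Protocol's rationale reports 10% dropout for side effects in both earlier studies of SXB in Parkinson's disease. The offer of active drug after dropout also gives a placebo participant without benefit a reason to leave. With 12 per arm, two such people in an arm matter.

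**Working it through.** **1. The plan's own figure.** Placebo mean 10.3 and SD 3.7 episodes per month, and a 50% reduction (Protocol, sample size section); two-sided alpha 0.05 (SAP); power 80%. The active-arm SD is not given, so 3.7 is assumed for both arms.
- Difference: 10.3 × 0.5 = 5.15.
- Normal approximation: n = 2 × (1.96 + 0.84)² × 3.7² / 5.15² = 8.1, so 9 per arm. The t-based calculation gives 10 per arm (power 83.7%). The stated 10 reproduces.
- Enrolment: 20 / 0.85 = 23.5, so 24. At 20% dropout, 20 / 0.80 = 25, or 24 by 20 × 1.20. The stated 24 is not in dispute.

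**2. How many participants.** 24 × 0.15 = 3.6 and 24 × 0.20 = 4.8, or 1.8 to 2.4 per arm. These are upper limits for the number without a retrieved post-baseline log, because some dropouts will leave after Visit 3.

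**3. Time to the first log collection.** Day 57 − Day 29 = 28 days; Day 85 − Day 29 = 56 days. That is about 4 to 8 weeks after first dose, before the ±7-day window. Anyone who stops within four weeks cannot supply a full blinded month.

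**4. Stoppers left out.** Assume placebo stays at 10.3, SXB completers are at 5.15, SXB stoppers return to 10.3, and a fraction d stops. The all-assigned difference is (1 − d) × 5.15.

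| d | All-assigned difference | 5.15 ÷ that | Overstatement |
|---|---|---|---|
| 10% | 4.64 | 1.11 | 11% |
| 15% | 4.38 | 1.18 | 18% |
| 20% | 4.12 | 1.25 | 25% |

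**5. Open-label values counted as randomised.** Assume placebo dropouts gain the full SXB effect and SXB dropouts keep theirs.
- At 15%: placebo mean 0.85 × 10.3 + 0.15 × 5.15 = 9.53; difference 9.53 − 5.15 = 4.38.
- At 20%: placebo mean 0.80 × 10.3 + 0.20 × 5.15 = 9.27; difference 4.12.
- The figures match step 4 because both equal (1 − d) × 5.15, but here they are the estimate, pulled below 5.15 by rescue in the placebo arm.
- Power with 12 per arm (t test, SD 3.7 plus mixture variance) falls from 90.3% without dropout to 74.3% at 15% and 67.9% at 20%.

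**6. Both assumptions together.** If SXB stoppers are at 10.3 and placebo dropouts gain the full effect, counting everything as randomised gives:
- 15%: 9.53 − (0.85 × 5.15 + 0.15 × 10.3) = 9.53 − 5.92 = 3.61.
- 20%: 9.27 − (0.80 × 5.15 + 0.20 × 10.3) = 9.27 − 6.18 = 3.09.

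Against the all-assigned difference without rescue (4.38 and 4.12), leaving stoppers out gives too large a figure (5.15) and counting open-label nights gives too small a one (3.61 and 3.09).

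**The case against.** The best reply is that the protocol already has much of what is needed.
- The log runs at home for 14 weeks from Day 1, so blinded nights before a stop should be on paper, and a mixed model can use them under a missing-at-random assumption.
- Weekly calls record response and adverse events within days of any stop.
- CGI-E and CGI-I are defined on the last day of treatment, which can be read as the stopping day.
- If returning at Visit 2 means repeating that visit, a rescue entrant hands in a log and an Epworth score before open-label dosing.

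Most of this stands, and it limits the point. A reader might infer that dropouts are followed only if they switch, that nothing is assessed when drug stops, or that the analysis has no unconfounded data for stoppers. The documents support none of these. They are silent about other dropouts rather than barring follow-up, and the pre-stop log should exist.

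The gap remains. No step clearly retrieves the log from a dropout who does not enter the open-label period. For one who does, the Visit 2 wording is ambiguous: it may restart the schedule, which would detach later visits from the randomisation date, or only mark which visits still apply. CGI is scheduled only at Visits 3 and 4, so an early stopper has no listed contact for it. The two weeks of data after discontinuation follow the planned end of fixed dosing.

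A reader might also infer that the trial will overstate the effect of SXB. That holds under one handling of the data and is reversed under another. The return of SXB stoppers to 10.3 is an assumption that the documents do not support or contradict.

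**Conclusion.** The point holds in this form: the only follow-up described after dropout is on open-label SXB, no assessment is specified when blinded drug stops early, and the SAP does not say how pre-stop, off-drug or open-label logs enter the intention-to-treat analysis. Early stoppers may therefore contribute no retrieved post-baseline log, or only data confounded by unblinded SXB.

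Up to 3.6-4.8 of 24 participants are affected at the planned dropout rate. The 18-25% overstatement is illustrative. It requires that all stoppers are left out and that those on SXB return to the placebo mean. The opposite error is possible if open-label nights are counted as randomised. The change is worth making because it is cheap and the SAP's main claim depends on it. The sample size itself is not in question.

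**What to change.** Separate stopping blinded drug from leaving the study.

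1. **At the stop.** Retrieve the RBD log to date and complete CGI-E, CGI-I, ESS, PSQI, PHQ-9, GAD-7 and adverse events, by phone or video if needed. Aim to do this before open-label nights begin, but do not make it a condition of any treatment or let it delay treatment. The log has priority: the SAP analyses the secondary and exploratory outcomes per protocol, so the log is what serves the primary analysis.
2. **After the stop.** Ask everyone who stops, with or without open-label SXB, to keep the log and return it at fixed times counted from randomisation, because Visits 3 and 4 move with titration. Record the date of any open-label start. Clarify what returning from Visit 2 means.
3. **In the SAP.** State that pre-stop blinded logs and off-drug logs enter the intention-to-treat model as randomised. State that open-label nights are flagged and not counted as blinded randomised treatment, with a sensitivity analysis that includes them. Define which month from randomisation stands in for the last month of treatment when someone stops early; without this, off-drug logs have no place in the endpoint.

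No extra polysomnography is needed, and consent may still be withdrawn. The cost is protocol and SAP wording plus one contact for about 4-5 participants. Some will decline, and the estimated effect may be smaller. The flag does not recover what a rescued participant would have reported without SXB; it only keeps those nights from being mistaken for blinded treatment.
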